**Exploratory end point:**

QoR 15: The QoR 15 will be administered in the form of a questionnaire to be filled out by the participants at 24 hours ( $\pm 2$  hours) postoperatively for the purposes of validation.

**Sample size calculation**

The primary outcome will be the mean OBAS score measured at 24 hours postoperative. Using a non-inferiority margin of +3 points, SD of 5, power of 90%, and 1-sided two-sample equal variance t-test with an alpha of 0.05, the sample size is 49 participants per group, 98 participants total. If it is determined after randomization that a participant will need an additional spinal injection, they will be evaluated for data. We will perform intention-to-treat analysis including these participants as well as per-protocol analysis excluding them. Based on our data, this would be a rare situation as <1% of our current patients need a spinal. The sample size will be increased by 5% to maintain power for the per-protocol analysis. Increasing the sample size by 5% changes the sample size to 52 subjects per arm, for a total of 104 subjects.

We will pilot the OBAS in our target population (20 patients) in order to obtain an estimate of the SD specific to our patient population. The SD reported in the literature varies from 2 to 4, so we used an SD of 5 in our calculation in order to be conservative. A SD of 4 would require 32 patients per group. Prior to the enrollment of the first patient in this trial, a modification will be submitted to the institutional review board if the pilot data prompts us to modify sample size.

**Statistical analysis plan**

Data will be summarized using standard descriptive statistics by reporting mean (SD) or median (IQR) for continuous variables and frequency and percentages for categorical variables. Continuous variables will be compared between the two treatment arms using the two-sample t-test or the Wilcoxon rank sum test as appropriate. Categorical variables will be compared between the two treatment arms using the chi-square test or the Fisher's exact test. For the primary outcome, the mean OBAS score between the two groups will be presented along with the upper limit of the 95% confidence bound for the mean difference. We will conclude non-inferiority if this upper limit is less than the predefined limit for non-inferiority. Multivariable regression models will be fit to assess for differences in outcomes if there are unbalanced baseline covariates in the two treatment arms.

The primary analysis will be restricted to per-protocol patients and will mirror that of the POP-UP trial, which was a non-inferiority trial that evaluated the effectiveness of continuous wound infiltration in patients undergoing hepato-pancreato-biliary surgery. An intention-to-treat analysis will be performed as a secondary analysis based on the rationale that such an analysis in a non-inferiority trial might introduce bias to no difference.

A thorough review of the data for inconsistencies and outliers will be performed by the statistical team prior to the formal analysis. Data issues will be resolved by the primary investigator and study coordinator. The extent of missing data will be examined and sensitivity analyses of the primary and secondary outcomes will be conducted using multiple imputation if warranted. All statistical analyses will be performed using SAS or R.

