**Outcomes:**

Primary outcome:

Overall Benefit of Analgesia Score (OBAS): The OBAS will be administered in the form of a questionnaire to be filled out by the participants at baseline (preoperatively) and at 24 hours ( $\pm 2$  hours) postoperatively. The OBAS consists of 7 items that assess pain intensity, opioid-related adverse effects and patient satisfaction with pain management. The composite score ranges from 0 (best) to 28 (worst).

Secondary outcome:

Cumulative 24 hour narcotic consumption, measured in morphine metabolic equivalents (MME)

Postoperative pain scores (rest, movement) at 4, 8, 16 and 24 hours after surgery.

Time to first analgesic request

Use of intravenous patient-controlled analgesia

Use of IV rescue opioids

Length of stay

Fluid balance: Additional fluid requirement after 24 hours of surgery, weight gain following surgery

Cost of care

Adverse events:

Related to spinal injection: Puncture site bleeding/hematoma/infection; Spinal headache

Related to systemic opioid effects: Itching; Nausea/vomiting; Sedation; respiratory depression

Related to delayed recovery: Time to regular diet/Bowel movement, postoperative ileus, time to first ambulation, time to Foley removal, voiding dysfunction/ need for re-catheterization, readiness for discharge

Cost analysis:

OR time and surgical time

Total and pain management related standardized costs

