### Postoperatively in the PACU:

1. Fentanyl orders in the PACU: 25 mcg IV Q 2minutes prn pain 4 or greater up to 100 mcg maximum. If max dose of fentanyl is reached, discontinue fentanyl and give intravenous hydromorphone. Hydromorphone0.2 mg Q 5 minutes IV prn pain score 4-10 up to 2 mg maximum.
2. If maximum opioids are reached in the PACU, further opioid prescribing is per the discretion of the anesthesiologist.
3. Ketamine 10 mg IV may be given prn breakthrough pain at the anesthesiologist's discretion.
4. Rescue antiemetics, droperidol, Zofran, Kytril at the anesthesiologist's discretion.

5. Caffeine 250 mg IV will only be given at the anesthesiologist's discretion.
6. Ditropan: 5 mg po once as needed for bladder spasms
7. Demerol: 12.5 mg IV Q 15 min prn shivering up to 2 doses maximum.
8. Acetaminophen 1000 mg IV or po, if 6 or more hours have passed since the preoperative dose.
9. Ketorolac 15 mg IV may be given if stratified to "plan for NSAID use" at the anesthesiologist's discretion if it was not previously given in the OR.

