#### **Appendix B. Postoperative pain Management**

1. Tylenol 1000mg po every 6 hours
2. Ketorolac 15 mg IV every 6 hours X 4 doses if stratified to "plan for NSAID use"
3. Ibuprofen every 6 hours if stratified to "plan for NSAID use", start 6 hours after the last Ketorolac dose. See table below for dose.

Ibuprofen dose	Weight <50 kg	Weight 50-80 kg	Weight >80 kg
Age <65	200	600	800 q 8 hours
Age >65	200	400	600

4. Oxycodone 5mg every 4 hours PRN for moderate pain or pain score of 4-6/10. Administer if pain is unrelieved by Tylenol. For patients who received intrathecal analgesia, start 24 hours after intrathecal dose was given.
5. Oxycodone 10mg every 4 hours PRN for severe pain or pain score of 7-10/10. Administer if pain is unrelieved by Tylenol. For patients that received intrathecal analgesia, start 24 hours after intrathecal dose was given.
6. Dilaudid 0.4mg IV every 2 hours PRN for breakthrough pain. To be given if pain is unrelieved 30 minutes after PRN oral medication is used; if unable to take oral pain meds; or if pain is greater than or equal to 7, use instead of oral pain medication.
7. Oral intake, timing of Foley catheter removal and ambulation in accordance to ERAS protocol and discretion of the surgeon.

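### Time to first analgesic request has no rule for patients who never request, so a literal t-test or Wilcoxon comparison is confined to requesters and may be biased

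*Combined protocol and SAP*

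**What the plan says.** Section C.2, Outcomes, lists "Time to first analgesic request" among the secondary outcomes. It gives no time zero, observation window, qualifying drug or value for a patient who never asks. The same list contains "Use of IV rescue opioids", "Use of intravenous patient-controlled analgesia" and cumulative 24-hour opioid consumption.

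The Statistical analysis plan does not name this outcome. Its rule for continuous variables is "Continuous variables will be compared between the two treatment arms using the two-sample t-test or the Wilcoxon rank sum test as appropriate"; categorical variables get chi-square or Fisher tests. No Kaplan-Meier, log-rank, Cox or censoring rule appears. On absent values it says only that "sensitivity analyses of the primary and secondary outcomes will be conducted using multiple imputation if warranted".

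Appendix B, items 4 and 5, times oral oxycodone differently by arm: "For patients who received intrathecal analgesia, start 24 hours after intrathecal dose was given". Other opioid orders carry no such arm-specific delay: "Dilaudid 0.4mg IV every 2 hours PRN for breakthrough pain" (Appendix B, item 6) and "Fentanyl orders in the PACU: 25 mcg IV Q 2minutes prn pain 4 or greater up to 100 mcg maximum" (Appendix A, PACU).

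**The concern.** This is a time-to-event outcome assigned, by elimination, to a rule for ordinary continuous measurements. Someone who needs nothing in the window is event-free, not missing, but software given a blank time will drop her. The comparison is then conditioned on an outcome that treatment can change. The Background expects ITA to give more intensive relief in the first 24 hours, so the patients removed could be those who benefited most, and more of them could come from the ITA arm. The result could hide a real difference or even point the wrong way. Imputing a request time would not help, because it invents an event that did not happen.

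The trial is unblinded. If the handling is left open, it will be chosen by people who can see the allocation.

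**Working it through.** **Inputs from the documents.** The final size is 52 per arm (Sample size calculation), allocated 1:1. That size is for OBAS: margin 3, SD 5, one-sided 0.05, power 90%. The normal approximation gives 2 × 25 × (1.645 + 1.282)² / 9 = 47.6, or 48 per arm. The exact noncentral-t calculation gives 49 (power 0.904), as stated, and 49 × 1.05 = 51.45 rounds up to 52. The plan's figure reproduces. No power is stated for time to first request.

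**Assumptions.** All request rates and times are assumed. The 24-hour cut-off is borrowed from the opioid-consumption outcome. Tests are two-sided at 0.05, since no level is stated for secondary outcomes. Three analyses were simulated: log-rank with never-requesters censored at 24 h, Wilcoxon with them tied last, and Wilcoxon on requesters only.

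**Never-request shares under a constant hazard ratio of 0.5.** With exponential times, the ITA share equals the incisional-only (ILB) share to the power 0.5: √0.05 = 0.22 and √0.40 = 0.63.

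**Cross-check on the log-rank figures.** Power is approximately Φ(√(d/4) × |ln HR| − 1.96), where d is the expected number of requests.
- At 5% never in ILB: d = 52 × 0.95 + 52 × 0.78 = 90; √22.5 × 0.693 − 1.96 = 1.33; power about 0.91.
- At 40%: d = 52 × 0.60 + 52 × 0.37 = 50; √12.5 × 0.693 − 1.96 = 0.49; power about 0.69.

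The simulated values are 0.90 and 0.68.

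**Simulated power**

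| Scenario (never request, ILB vs ITA) | Log-rank | Ranked last | Requesters only |
|---|---|---|---|
| HR 0.5, 5% vs 22% | 0.90 | 0.84 | 0.40 |
| HR 0.5, 20% vs 45% | 0.84 | 0.79 | 0.15 |
| HR 0.5, 40% vs 63% | 0.68 | 0.66 | 0.07 |
| Same timing, 5% vs 30% | 0.86 | 0.60 | 0.06 |
| Same timing, 10% vs 40% | 0.92 | 0.77 | 0.05 |
| Mean 4 vs 8 h, 5% vs 25% | 0.99 | 0.98 | 0.79 |
| Mean 4 vs 8 h, 20% vs 50% | 0.975 | 0.98 | 0.64 |
| Mean 4 vs 8 h, 50% vs 75% | 0.83 | 0.86 | 0.39 |
| Mean 4 vs 8 h, 5% vs 5% (delay only) | 0.65 | 0.76 | 0.83 |

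With no treatment effect, all three tests reject close to 5% of the time. In the delay rows, times are capped just inside 24 h; handling the tail otherwise moves these figures by several points.

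**The direction can reverse.** Suppose 40% of ILB and 30% of ITA patients request evenly over 0 to 2 h, 45% and 20% evenly over 2 to 24 h, and the rest never do.
- Among requesters, the ILB median falls at cumulative share 0.85/2 = 0.425, so 2 + 22 × 0.025/0.45 = 3.2 h. The ITA median falls at 0.25, so 2 × 0.25/0.30 = 1.7 h.
- Over all patients, the ILB median is 2 + 22 × 0.10/0.45 = 6.9 h. The ITA median sits at the edge of the window (23.9 h as simulated).

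Requesters alone suggest that ITA patients ask sooner; the full arms show the opposite.

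**What other planned outcomes retain.** If 30% to 80% of requesters in each arm receive IV rescue, a chi-square test on IV rescue use has power of 10% to 57% under hazard ratio 0.5, and 15% to 73% in the two same-timing rows. Opioid consumption and PCA use were not computed.

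**The case against.** The strongest reply is that the plan never says never-requesters will be dropped. That is right: a reader might infer such an instruction, but the text is silent, and a Wilcoxon test that ranks these patients last is compatible with it. In most rows above, ranking last keeps power close to the log-rank test. The defect is the missing rule, not the choice of Wilcoxon.

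A reader might also infer that the comparison generally loses most of its power. The documents give no request rates, so they cannot support that. With delay alone, requesters-only is the strongest of the three tests and log-rank the weakest. With lognormal times (medians 4 vs 7 h, log-SD 0.8; 10% vs 30% never requesting), requesters-only power is 0.86 against 0.97. At hazard ratio 0.5 with only 1% of ILB patients never requesting, it is 0.64 against 0.92. What survives is that the loss can be large, and that conditioning on requesters risks bias whether or not power is lost.

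A third tempting inference is that the later oxycodone start in the ITA arm by itself distorts this outcome. That depends on what counts as a request. If only administered oral doses count, the arms could differ through the ordering rule alone; if requests for IV or PACU opioids count, the effect may vanish. With identical need in both arms, assumed inputs gave false rejection from about 5% to 87%, which is too wide to be evidence of size.

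Finally, this is one unpowered secondary outcome, and opioid consumption and IV rescue use include every patient. That stands and limits the priority. PCA use probably adds little, since the Background reports 4.1% use with liposomal bupivacaine.

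**Conclusion.** The point holds in limited form. The plan has no rule for patients who never request, and its only applicable test, run literally, is restricted to a group formed after randomization. Possible selection bias is the firmer harm; the loss of power depends on the scenario. It is large if ITA acts mainly on who ever requests or as a constant hazard ratio of 0.5 with 5% to 40% of ILB patients never requesting. It is moderate in the delay-and-prevention rows where at least half of each arm requests, and larger where only 50% and 25% do. It is absent where nearly everyone requests and ITA only delays. All of this rests on assumed rates, a 24-hour window and two-sided 0.05.

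Nothing here touches the OBAS sample size or the non-inferiority conclusion, and a reader should not infer otherwise. Low priority.

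**What to change.** Add to the Statistical analysis plan, before any outcome data are seen:

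- Analyse time to first analgesic request in all patients of the stated analysis set, from a named time zero to a common cut-off.
- Censor patients with no request at the cut-off; do not drop them or impute a time.
- Report Kaplan-Meier curves, a log-rank test and the event-free proportion by arm. Stratifying by the randomization factors is optional: in the same-timing rows it changed power only from 0.86 to 0.83 and from 0.92 to 0.91.
- A Wilcoxon test with never-requesters ranked last at the cut-off is an acceptable alternative. Name one of the two as the analysis, since neither is stronger in every scenario.
- Define a qualifying request identically in both arms, including whether PACU opioids count. Reconcile that definition with the arm-specific oxycodone timing in Appendix B, leaving every dosing rule as it is.

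The cost is a few sentences, a little more analysis work and a check that request times are captured. The sample size and treatment do not change.

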Given that visceral pain which can be significant in tumor debulking is not targeted by incisional bupivacaine, combining ITA with incisional liposomal bupivacaine (ILB) to provide more intensive pain relief in the first 24 hours is a viable option. However, it is unclear if patient experience with pain management is improved with ITA given that opioid related side effects (nausea, vomiting, itching) as well as rare adverse events related to spinal injections (postural puncture headache) can occur. Additionally, ITA is invasive and expensive. The purpose of this investigation is to evaluate whether ILB is non-inferior to a combination of ITA and ILB for management of postoperative pain after laparotomy for gynecological malignancy within an established enhanced recovery pathway using the Overall Benefit of Analgesia Score (OBAS) as our primary outcome. Additionally, we will evaluate cumulative 24 hour postoperative morphine milligram equivalents (MME) consumption, pain scores, length of stay, cost, and patient satisfaction as secondary outcomes.

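### Spinal-injection harms fall under a general between-arm chi-square or Fisher test that is uninformative against a near-zero comparator, and no confidence interval is planned for them

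*Combined protocol and SAP*

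**What the plan says.** The adverse events under Outcomes (section C.2) include a group tied to the procedure: "Related to spinal injection: Puncture site bleeding/hematoma/infection; Spinal headache". Opioid effects such as itching, nausea or vomiting, sedation and respiratory depression form a separate group. Under Intervention and Comparator, only the ITA arm is assigned a spinal injection.

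The Statistical analysis plan has no section on adverse events. Its general rule is to summarize categorical variables by count and percentage and then test them: "Categorical variables will be compared between the two treatment arms using the chi-square test" or Fisher's exact test. It does not say how to choose between the two tests, and it gives no significance level or sidedness for them. The only interval in the plan is the upper confidence limit for the OBAS mean difference.

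Two other places matter. The Background says that "rare adverse events related to spinal injections (postural puncture headache) can occur", as part of the reason it is unclear whether ITA improves patient experience. The Sample size calculation foresees that a few randomized patients may need an unplanned spinal (under 1% on current practice). It keeps them in the intention-to-treat analysis and removes them from the per-protocol analysis.

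**The concern.** A puncture-site complication or a spinal headache needs a puncture. In comparator patients treated as assigned, the rate is zero by construction. Whether the arms differ is therefore not the question of interest. The useful quantity is how often these harms occur in patients who have a spinal, and how precisely the trial can say so. The planned test does not address that, and no interval is planned that would.

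The trial asks whether ITA can be omitted, so the harms of ITA are one side of that judgement. A table showing a small count with a large p-value, and no interval, gives the reader no sense of how high the true rate could be.

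**Working it through.** **Inputs.** From the Sample size calculation: "the sample size is 49 participants per group, 98 participants total", then "Increasing the sample size by 5% changes the sample size to 52 subjects per arm, for a total of 104 subjects". The one-sided 0.05 level given there belongs to the primary comparison. No level is stated for categorical tests, so two-sided 0.05 is assumed below and one-sided 0.05 is shown as a variant. The documents give no expected rate for any spinal-injection harm.

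**The plan's own figure.** For margin 3, SD 5, power 90% and one-sided 0.05, the normal approximation is 2 × (1.645 + 1.282)² × 25 / 9 = 47.6, or 48 per arm. The exact t-test calculation gives 49 (power 0.904), as stated. Then 49 × 1.05 = 51.45, rounded up to 52, also as stated. The plan has no figure for the harms comparison.

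**Test of x/52 (ITA) against 0/52 (comparator).**
- Uncorrected chi-square = 104x / (104 − x).
- Yates chi-square = 104(x − 1)² / [x(104 − x)].
- Fisher, one-sided: p = C(52, x) / C(104, x). The arms are equal in size, so the two-sided p is twice this.
- Exact (Clopper-Pearson) 95% limits for the ITA rate. At x = 0 the upper limit is 1 − 0.025^(1/52) = 6.85%.

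| Events in ITA | Observed rate | Uncorrected chi-square p | Yates p | Fisher p (two-sided) | Exact 95% CI |
|---|---|---|---|---|---|
| 0/52 | 0% | – | – | – | 0 to 6.85% |
| 2/52 | 3.8% | 0.153 | 0.475 | 0.495 | 0.47 to 13.21% |
| 3/52 | 5.8% | 0.079 | 0.241 | 0.243 | 1.21 to 15.95% |
| 4/52 | 7.7% | 0.041 | 0.126 | 0.118 | 2.14 to 18.54% |
| 5/52 | 9.6% | 0.022 | 0.067 | 0.057 | 3.20 to 21.03% |
| 6/52 | 11.5% | 0.012 | 0.036 | 0.027 | 4.35 to 23.44% |

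The largest non-significant observed rate is 5.8% for uncorrected chi-square and 9.6% for Fisher or Yates. One-sided Fisher at 0.05 falls between them: p = 0.059 at 4/52 and 0.028 at 5/52, so its largest is 7.7%. The expected count in each event cell is x/2, which is at most 3 in this table, so Fisher is the usual choice. At 4/52 and 5/52 the result is significant or not depending on which of the two permitted tests is used.

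**Chance of a significant result, by assumed true ITA rate** (binomial, n = 52, no comparator events):

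| True rate (assumed) | Fisher (6 or more events) | Uncorrected chi-square (4 or more events) |
|---|---|---|
| 3% | 0.5% | 7.0% |
| 5% | 4.5% | 26% |
| 10% | 42% | 78% |

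**Sensitivity to an unplanned spinal.** If one comparator patient had a spinal-related event, Fisher would stay non-significant up to 7/52 (13.5%, p = 0.060).

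**The case against.** The strongest reply is that no information is lost. The plan commits to counts and percentages, so the ITA rate will be visible and anyone can work out an exact interval from x and n. The test comes from a general sentence on categorical variables and is not a specific plan to test these harms. The aims contain no safety hypothesis, and nothing says that non-significance will be read as safety. All of this stands. It makes the point one of reporting, but it leaves the plan with an uninformative test and no stated measure of precision.

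A reader might infer several stronger things that the documents do not support.
- *That these harms cannot occur in the comparator arm.* This holds for treatment as assigned and for the per-protocol set. The intention-to-treat set keeps patients with unplanned spinals, so there the rate is near zero and not necessarily zero.
- *That the null hypothesis has no meaning.* Equality with a near-zero rate is a well-defined null. Testing it is simply not useful.
- *That rates up to nearly 10% will be non-significant under the plan.* That is the Fisher or Yates end of a range starting at 5.8%, and it needs an assumed two-sided 0.05 level.
- *That the test will almost always be non-significant.* With Fisher this fits true rates up to about 5%; at 10% the chance of significance is 42%. The Background calls spinal-injection events rare, so the lower rates are the relevant ones, but the documents give no figure.
- *That these harms are the only reason given for questioning ITA.* The Background also cites opioid side effects, invasiveness and expense.

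Opioid-related harms are also not left wholly to a bare test. The OBAS includes opioid adverse effects and has a confidence limit. It is a composite, however, and gives no estimate for any single harm.

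**Conclusion.** The point holds as a reporting weakness. Applied as written, the general rule tests spinal-injection harms against a comparator assigned no puncture, and no interval is planned for them. With 52 per arm, no comparator events and two-sided 0.05, observed rates up to 5.8% (uncorrected chi-square) or 9.6% (Fisher) would be non-significant. No events at all would still allow a true rate up to 6.85%. A non-significant result therefore says little about the safety of the puncture.

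The thresholds rest on the assumed level and sidedness, and on the choice of test, which the plan leaves open. The primary analysis and the sample size are unaffected. The change is still worth making before analysis, because it replaces an uninformative comparison with the estimate that readers need.

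**What to change.** In the Statistical analysis plan, add a short paragraph on adverse events:

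- Do not test spinal-injection harms between arms. Report each as n/N (%) among patients who received a spinal puncture, with an exact (Clopper-Pearson) 95% confidence interval. This denominator also deals with unplanned spinals in the comparator arm.
- For opioid-related harms that can occur in both arms, report the risk difference with a 95% confidence interval (Newcombe or Miettinen-Nurminen) alongside any test.
- State that a non-significant test is not evidence of equal safety.

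The cost is a few lines of SAP text and code. No new data are needed, and neither the sample size nor the primary analysis changes.

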### **C. Research plan and methods:**

#### **C.1 Study design:** Randomized controlled study

##### Randomization:

1. Stratified by:
  - a. Likelihood of bowel resection  $\geq 50\%$  or  $<50\%$  as assessed by surgeon
  - b. Planning to use NSAIDs vs not planning to use NSAIDs
2. Allocation ratio- 1:1
3. Allocation sequence- permuted block randomization with varying block sizes ( Provided by statistician in the Department of Biostatistics and Informatics)

Blinding: None

Allocation concealment method: web-based

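### The bound that decides non-inferiority ignores the stratification factors and the baseline OBAS, and adjustment depends on an undefined imbalance trigger

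*Combined protocol and SAP*

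**What the plan says.** Under Randomization, allocation is 1:1 in permuted blocks, stratified by the surgeon's assessment of bowel-resection likelihood (at least 50% or below) and by "Planning to use NSAIDs vs not planning to use NSAIDs". There is no blinding. Under Outcomes, the OBAS questionnaire is "filled out by the participants at baseline (preoperatively) and at 24 hours" after surgery.

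Under Sample size calculation, "The primary outcome will be the mean OBAS score measured at 24 hours postoperative". The trial is sized with a margin of +3, SD 5, 90% power and a "1-sided two-sample equal variance t-test with an alpha of 0.05". This gives 49 per group, raised to 52 per arm (104 in total).

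Under Statistical analysis plan, the bound for the mean difference is presented, and then: "We will conclude non-inferiority if this upper limit is less than the predefined limit for non-inferiority". The per-protocol set is primary. No covariate is named. The only mention of adjustment is: "Multivariable regression models will be fit to assess for differences in outcomes if there are unbalanced baseline covariates in the two treatment arms". No other section gives an adjusted primary model, a covariate list or a criterion for imbalance.

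**The concern.** There are two linked problems.

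**The analysis does not follow the design.** Stratified randomization removes chance imbalance on the two factors, but the unadjusted standard error still counts the variation they explain. If the factors predict OBAS, the bound is wider than it needs to be and the test runs below its stated 5% level. Planned NSAID use is a plausible predictor because scheduled analgesia differs by stratum within the assessment window. Appendix B gives "Ketorolac 15 mg IV every 6 hours X 4 doses if stratified to" planned NSAID use. Leaving out baseline OBAS costs precision only, not validity.

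**The trigger for regression is open.** Imbalance would be judged after the data are seen, in an open-label trial, without a stated criterion or covariate list. The sentence refers to outcomes in general, so it does not exclude the primary one. It reads most naturally as supplementary to the decision rule, but the plan does not say so.

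Because the upper bound decides the trial, there should be only one way to calculate it.

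**Working it through.** **Inputs from the documents:** margin 3, SD 5 (alternative 4), one-sided alpha 0.05, 49 per group before and 52 per arm after the 5% increase, two binary stratification factors, 1:1 allocation. **Assumed, because the documents do not give them:** the share of 24-hour OBAS variance explained (R²), shown over a range; in the simulations, stratum prevalences of 30% and 70%, strata variance split equally between the factors, blocks of 2, 4 and 6, and normal outcomes.

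**1. The plan's own figure.** For n per group, SE = SD × √(2/n), and power at no true difference comes from the noncentral t with noncentrality 3/SE on 2n − 2 degrees of freedom.
- n = 49, SD 5: SE = 1.010, noncentrality 2.970, power 90.4%. The stated 49 reproduces.
- n = 32, SD 4: SE = 1.000, noncentrality 3.000, power 90.7%. The statement "A SD of 4 would require 32 patients per group" reproduces.
- n = 52, SD 5: SE = 0.981, noncentrality 3.059, power 91.8%.

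**2. Actual level of the unadjusted test.** If the strata explain R² and are balanced by design, the true variance of the difference is (1 − R²) times what the t-test assumes. The one-sided error is then approximately P(t₁₀₂ > t₀.₉₅,₁₀₂ / √(1 − R²)), with t₀.₉₅,₁₀₂ = 1.660. At R² = 10%, 1.660/√0.90 = 1.750, which gives 4.2%.

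**3. Distance from estimate to bound at 52 per arm.** Unadjusted: 1.660 × 5 × √(2/52) = 1.63 points. Adjusted for the strata: 1.660 × 5√(1 − R²) × √(2/52).

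The simulated columns come from 48,000 trials of 104 patients per scenario (Monte Carlo error about 0.1 point), with error at a true difference of 3 and power at 0.

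| Strata R² (assumed) | Unadjusted error, formula | Unadjusted error, simulated | Adjusted distance to bound | Power, unadjusted | Power, strata-adjusted |
|---|---|---|---|---|---|
| 2% | 4.8% | 4.7% | 1.61 | 91.9% | 92.2% |
| 5% | 4.6% | 4.5% | 1.59 | 92.2% | 92.8% |
| 10% | 4.2% | 4.1% | 1.54 | 92.7% | 93.9% |
| 20% | 3.3% | 3.4% | 1.46 | 93.7% | 95.9% |

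Strata adjustment restores the error to about 5%.

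**4. Adding baseline OBAS to the strata (simulated, 52 per arm, SD 5).**
- Baseline alone prognostic, R² 5%: unadjusted error 4.9%; power 91.7% to 92.6%.
- Strata 5% plus baseline 5%: power 92.2% to 93.7%.
- Nothing prognostic: power 91.7% to 91.5%.

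**5. If the SD is 4.** At 52 per arm, unadjusted power is already 98.4%. At 32 per group it is 90.7% unadjusted, and 91.9%, 93.1% and 95.3% adjusted at total R² of 5%, 10% and 20%.

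**6. Worst case for the trigger.** Suppose the more favourable of the unadjusted and fully adjusted bounds were used. Over 12,000 simulated trials per scenario (simulation error about 0.2 points), one-sided error was 5.2% with nothing prognostic, 5.8% with strata 5% plus baseline 5%, 7.0% with baseline alone at 20%, and 4.9% with strata alone at 20%.

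**The case against.** The strongest reply is that nothing here is an error. The planned test matches the sample-size test, the stated size reproduces, and the test is valid and at worst slightly conservative. That stands: this is a point about efficiency and pre-specification.

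The gain may also be small. The plan puts literature SDs at 2 to 4 and chose 5 to be cautious; at SD 4 and 52 per arm there is little left to gain. The high R² values are demanding. With the assumed prevalences and equal split, each factor's shift in mean OBAS is √(25 × R²/2 ÷ 0.21): about 2.4 points at 10% and 3.45 points at 20%, the latter above the margin itself. Preoperative OBAS may predict weakly, since its items include opioid side effects and satisfaction with pain management. Appendix A also lists preoperative Celebrex without restriction by stratum, which may narrow the NSAID contrast. All this is fair, and the low end of the range is the more likely. It limits the benefit but creates no cost, because including a useless covariate loses almost nothing.

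Three further points are minor.
- The simulations use all 104 patients, whereas the per-protocol set is primary. With 49 per group, power is 90.4% unadjusted and 91.6%, 92.8% and 95.1% at total R² of 5%, 10% and 20%, so the picture is the same.
- The plan says its primary analysis mirrors an earlier wound-infiltration trial. Whether that trial adjusted cannot be checked here, and the plan's own text specifies no adjustment.
- A missing baseline OBAS needs handling; simple baseline imputation suffices.

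Finally, the regression sentence can be read as supplementary, and the worst case in step 6 is not what the plan says it will do. But the wording does not rule it out.

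**Conclusion.** The concern holds. The deciding bound leaves out both stratification factors and a baseline measure that is already collected, and the only provision for adjustment has no criterion, covariate list or stated role. The risk of a false non-inferiority claim is not raised by the unadjusted test itself. At 52 per arm and SD 5, the gain from strata adjustment is about 0.3 to 0.6 points of power at strata R² of 2% to 5%, and 2.2 points at 20%. It would matter more if the pilot led to 32 per group, where there is little spare power.

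The size rests on R² values that the documents do not give, on the assumed stratum prevalences, and on reading the 95% bound as one-sided, in line with the stated alpha. The case for acting does not depend on a large R²: the change costs almost nothing and closes a data-dependent choice of model. It should be made, but the trial is not unsound without it.

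**What to change.** Before any outcome data are examined, amend the Statistical analysis plan as follows.

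1. Define the primary analysis as a linear model of 24-hour OBAS on arm, bowel-resection stratum, NSAID stratum and baseline OBAS. Compare the one-sided 95% upper bound of the adjusted mean difference with +3.
2. State how a missing baseline OBAS is handled, for example by simple imputation that does not use treatment arm.
3. Keep the unadjusted t-test bound as a sensitivity analysis.
4. Delete the imbalance-triggered regression, or label it supplementary, list its covariates in advance and state that it cannot change the non-inferiority conclusion.
5. For secondary outcomes, add stratum terms only for continuous outcomes where the data support them. Leave sparse adverse events and other rare binary outcomes unadjusted.

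The cost is SAP wording. Both strata and baseline OBAS are already collected, so no patients or visits are added. If no covariate is prognostic, the loss is about 0.2 points of power.
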